| | 
intervention arm) or against a composite reference standard that includes bacteriologically confirmation or/and clinical evidence resulting in therapy initiation.
 
 Diagnostic accuracy of CRP in blood compared to TB symptom's screening in those with microbiologically confirmed TB. 
Comparison of primary and secondary endpoints of the intervention arm with the local standard of care at the sites before the study initiation (a retrospective data collection from consecutive PLHIV admitted at participating hospitals).
 
Sub-analysis
 
 Primary endpoint will be calculated at different intermediate timepoints (48 hours, 7 days and 14 days from enrolment). Primary and selected secondary endpoints will be calculated for participants' subgroups including CD4 cells/mm³ ≥200, <200 and <100, among participants with any TB symptoms, severely ill participants or with AHD, and among participants providing at least one sputum and (or) one urine sample for testing. | | | | | | | | | | | | | | | | | | | | |
| Study Timeline | 
  
 Estimated period for ethics clearance	May / 2022	
 
 Import permits and importation	Jan-May / 2022	
 
 Kick off / training meeting	Nov / 2021	
 
 Estimated date of first participant enrolled:	Sep/ 2022	
 
 Estimated date of last participant enrolled:	Jan/ 2024	
 
 Estimated date of last participant completed:	Mar/ 2024	
 
 Estimated date for end of data cleaning:	May / 2024	
 
 Estimated date for end of data analysis:	July / 2024	
 
 Estimated date for first manuscript draft:	Sep / 2024	
 
 Total duration of study:	47 months	
  
 | Estimated period for ethics clearance | May / 2022 | Import permits and importation | Jan-May / 2022 | Kick off / training meeting | Nov / 2021 | Estimated date of first participant enrolled: | Sep/ 2022 | Estimated date of last participant enrolled: | Jan/ 2024 | Estimated date of last participant completed: | Mar/ 2024 | Estimated date for end of data cleaning: | May / 2024 | Estimated date for end of data analysis: | July / 2024 | Estimated date for first manuscript draft: | Sep / 2024 | Total duration of study: | 47 months |

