From Hospitalization Assessment TB-CAPT-HIV EXULTANT-Hospitalization assessment-v3, and the following versions of this document we will use for the analysis the next variables:

Variable		Used in
label	name	
Date of enrolment	ENROL_D	To calculate the participant's start time
Time of enrolment (24h format)	ENROL_T	
Date of discharge	HOSP_END_D	To calculate the participant's hospitalization time
Time of discharge (24h format)	HOSP_END_T	
Date of lab result: Sputum Ultra	SP_XP_RES_RECEPT_D	To calculate the time to obtain the laboratory results and classify the primary outcome $\leq 72$ h or $> 72$ h for Sputum Ultra sample
Time of lab result: Sputum Ultra	SP_XP_RES_RECEPT_T	

Date of lab result: Urine Ultra	URINE_XP_RES_RECEPT_D	To calculate the time to obtain the laboratory results and classify the primary outcome <= 72h or > 72h for Urine Ultra sample
Time of lab result: Urine Ultra	URINE_XP_RES_RECEPT_T	
Did the patient have cough during hospitalization?	HOSP_COUGH_YN	We will use to describe symptoms.  We will use as a factor variable in modelling
Did the patient have fever (>38°C) during hospitalization?	HOSP_FEVER_YN	We will use to describe symptoms.  We will use as a factor variable in modelling
Did the patient have night sweats during hospitalization?	HOSP_NIGHT_SWEATS_YN	We will use to describe symptoms.  We will use as a factor variable in modelling
Did the patient lose weight during hospitalization?	HOSP_WEIGHT_LOSS_YN	We will use to describe symptoms.  We will use as a factor variable in modelling
Was TB treatment initiated during hospitalization?	HOSP_TB_TX_YN	To calculate the primary objective variable, start treatment within 72h of enrolment
TB treatment initiated, Date and Time	HOSP_TB_TX_START_D HOSP_TB_TX_START_T	
If Yes, AND the patient has a microbiologically confirmed TB diagnosis (question 2.3), was the treatment initiated within 72hrs of enrolment?	HOSP_TB_TX_72H_YN	To determine the proportion of microbiologically confirmed TB cases starting treatment within 72 hours

If wasn't the treatment initiated within 72hrs of enrolment, reason	HOSP_TB_TX_72H_RSN HOSP_TB_TX_72H_RSN_SPEC	To determine the reasons behind starting treatment failure
---	---	--

The laboratory results we will be collected from (15) TB-CAPT-HIV EXULTANT-LabResults-v3- CRF, and the following version of this document. From this source we will select to study the following variables:

Variable		Used in
Label	name	

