## 5 Sample Size

We expect the absolute difference in proportions of bacteriological confirmation between the two arms to be 7% (from 19% to 26% from the control to the intervention arm). Sample size was chosen to be sufficient to detect a 36.8% relative increase in the primary outcome in the intervention arm (as compared to the control arm).

Under this premise and the following assumptions:

- Alpha (two sided): 0.05
- Beta (power 80%): 0.2
- Estimated proportions of participants with microbiologically confirmed TB in the control arm 19% and in the intervention arm 26%
- Lost to follow up: 5% of recruited participants.

The study will recruit 586 PLHIV participants per trial arm, then we will include in the analysis 1172 participants in total. This number of participants will come from 4 sites (293 participants per arm at each site).

For this calculation we have used the following formulas based on Normal asymptotic approximation for proportions:

Sample Size formula

$$n_1 = \frac{\left( Z_{1-\alpha/2} \sqrt{(1 + \varphi) \bar{p}_1 (1 - \bar{p}_1)} + Z_{1-\beta} \sqrt{\varphi p_1 (1 - p_1) + p_1 (1 - p_1)} \right)^2}{\varphi |p_1 - \bar{p}_1|^2}$$

Power formula

$$\varphi = \frac{1 - w_1}{w_1}$$

$$\bar{p} = \frac{p_1 + \varphi p_2}{1 + \varphi}$$

$$1 - \beta = \Phi \left( \frac{|p_1 - \bar{p}| \sqrt{\varphi w_1} - Z_{1-\alpha/2} \sqrt{(1 + \varphi) \bar{p} (1 - \bar{p})}}{\sqrt{\varphi p_1 (1 - p_1) + p_2 (1 - p_2)}} \right)$$

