### 6.3 Multiple Testing

We consider unnecessary to apply a general adjustment of significance level by multiple comparisons test. We will use the all the statistical power for inference only in the primary study objective. To evaluate the other study endpoints, we use the p-value threshold at 0.05 to find the differences in our study without the objective to extrapolate the results to the global community. However, we will establish a p-value of 0.01 as a threshold for statistical significance in the comparisons related to a) selected secondary efficacy analyses (section 8.2, analyses 8.2.5, 8.2.6, 8.2.7) and subgroup analysis (see section 9.0)

We will adjust the results by site, demographic variables, and other baseline variables if we will detect differences or if these variables have a confounder characteristics profile. To decide this, we will do a preliminary analysis of these variables between sites.

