## 8 Efficacy Analyses

### 8.1 Primary Efficacy Analysis

The primary efficacy is defined as the difference in the proportion of microbiologically confirmed TB and therapy initiated within 72 hours from enrolment in the intervention and control arm. (the comparison by estimating the difference of proportions and see whether is significantly differs from zero)

We will compare the difference of proportions, defined above, between both study arms and see if the results are significantly different from zero. We will test this differences using the test statistics  $z$  has an asymptotic standard normal distribution, and the p-value will be computed as:

$p = 2 \{1 - \Phi(|z|)\}$  where  $\Phi(\cdot)$  is the cdf of a standard normal distribution and  $|z|$  is an absolute value of  $z$ . We will calculate logit-transformed 95% confidence intervals

We will compare this proportion as a risk difference and we will stratify by study countries, baseline CD4 counts (under the hypothesis the highest difference in % of bac confirmed participants between control and intervention arm will occur in those immunosuppressed ones, or in countries with highest % of immunosuppressed admitted participants).

We will evaluate the primary efficacy analysis by ITT and Per protocol populations. We will show the both results in the final analysis document with the correspondent tables and graphs.

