## 9. Subgroup analysis

The analysis of all endpoints will be done for all patients of both countries as sample size did not take into consideration country-specific analyses of the specified primary endpoint. Thus, we will merge the data from the four sites we will analyse the resulting database as unique source of data.

However, a subgroup analysis of the primary endpoint and main secondary endpoint (mortality at month 2) will be done by study site (Mozambique and Tanzania, CD4 counts and viral load).

A separate analysis of the primary and secondary endpoints will also be performed by sex of participants, in order to assess if differences arise in any of the outcomes.

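### The SAP hypothesises a larger effect in immunosuppressed participants but specifies no treatment-by-subgroup interaction, and the symptom/severity subgroup in the Protocol synopsis is missing from Protocol 13.2.3 and SAP 9

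*SAP*

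**What the plan says.** - **Hypothesis.** SAP 8.1 will express the primary endpoint as a risk difference stratified by country and baseline CD4, "under the hypothesis the highest difference in % of bac confirmed participants between control and intervention arm will occur in those immunosuppressed ones". It extends this expectation to countries where a higher share of those admitted are immunosuppressed.
- **Subgroups.** SAP 9 states that "a subgroup analysis of the primary endpoint and main secondary endpoint (mortality at month 2) will be done by study site". Its parenthesis then names the two countries, CD4 and viral load, and a separate analysis by sex follows.
- **Threshold.** SAP 6.3 says "we will establish a p-value of 0.01 as a threshold for statistical significance in the comparisons related to" certain secondary analyses and the section 9 subgroup analysis. Protocol 13.2.2 also gives 0.01 for subgroup analysis.
- **Interaction.** Neither document names an interaction test or estimate. The nearest text, in Protocol 13.2.2, says that heterogeneity between sites will be examined. It gives no method and does not mention CD4.
- **CD4 categories.** SAP 7.2 uses two groups split at 100. SAP 11 uses three bands (below 100, 100-200, above 200) that may be refined on observed frequencies. Protocol 13.2.3 uses at least 200, below 200 and below 100, of which the last two overlap.
- **Symptom and severity subgroup.** The Protocol synopsis, under Sub-analysis, includes the endpoints "among participants with any TB symptoms, severely ill participants or with AHD". Protocol 13.2.3 and SAP 9 do not list this subgroup.
- **Symptom fields.** Those in SAP 4.4 come from the hospitalisation form, for example "Did the patient have cough during hospitalization". They are meant for description and as factors in modelling.

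**The concern.** Whether an effect is larger in one group than in another is a question about the difference between two risk differences. A p-value inside each stratum does not address it. With a 0.01 threshold and strata that are fractions of the trial, one stratum can easily cross the line while the other does not, even when the effects are equal. SAP 8.1 states in advance which stratum should show more, so a result in the low-CD4 stratum alone could be reported as confirmation.

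The second part concerns what the trial can say about its own design. Control testing is triggered by symptoms, serious illness or advanced HIV disease (Protocol 9 and 10.9.2), whereas the intervention arm is tested regardless (10.9.1). Splitting participants by those triggers would help to separate gain from testing people whom the control strategy would not test from gain due to extra specimens in people tested anyway. Symptoms recorded during the stay cannot define that split cleanly, because they are observed after randomisation in an unblinded trial.

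**Working it through.** **Inputs from the documents.** SAP 5 gives the significance level as "Alpha (two sided): 0.05", the power as "Beta (power 80%): 0.2", and the rates to be compared as "Estimated proportions of participants with microbiologically confirmed TB in the control arm 19% and in the intervention arm 26" (per cent). It also gives 5% loss and 586 per arm. SAP 6.3: 0.01 for subgroup comparisons. **Assumption:** a low-CD4 share of 30% to 60%, which the documents do not give.

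**1. The plan's sample size.** Pooled proportion 0.225.

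n = [1.960 × √(2 × 0.225 × 0.775) + 0.842 × √(0.19 × 0.81 + 0.26 × 0.74)]² / 0.07² = [1.960 × 0.5906 + 0.842 × 0.5885]² / 0.0049 ≈ 558 per arm.

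558 × 1.05 = 586, and 558 / 0.95 = 588. The stated 586 reproduces. With 586 × 0.95 ≈ 557 analysable per arm, power is 80.0%. Sample size is not in dispute.

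**2. Within-stratum power at 0.01 when the effect is 7 points in every stratum.** For m participants per arm in a stratum:

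power = Φ[(0.07 × √m − 2.576 × 0.5906) / 0.5885].

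Equal split, m = 278.5: (1.168 − 1.521) / 0.5885 = −0.600, so power is 27%.

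**3. How often the strata disagree.** With stratum powers a (low CD4) and b (high CD4), exactly one is significant with probability a(1 − b) + b(1 − a), and only the low-CD4 stratum with probability a(1 − b). Based on 557 per arm:

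| Low-CD4 share | Power, low CD4 | Power, high CD4 | Exactly one significant | Low CD4 only |
|---|---|---|---|---|
| 30% | 15% | 41% | 43% | 9% |
| 40% | 21% | 34% | 41% | 14% |
| 50% | 27% | 27% | 40% | 20% |
| 60% | 34% | 21% | 41% | 27% |

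There is no effect modification in any row. An interaction test would err at its nominal rate here.

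**4. Precision of the interaction.** Equal halves, no loss (293 per arm per half): SE of each risk difference = √[(0.1539 + 0.1924) / 293] = 0.0344. SE of their difference = 0.0344 × √2 = 0.0486, so the 95% CI is ±1.96 × 0.0486 = ±9.5 points. With 5% loss the SE is 0.0499, or ±9.8 points.

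The gap detectable with 80% power at 0.05 is (1.960 + 0.842) × 0.0499 ≈ 14 points. It is about 13 to 16 points over low-CD4 shares of 30% to 60%, with control rates of 19% in both strata or 28% in the low-CD4 stratum (both assumed) and 19% overall. For true effects of 10 and 4 points in equal halves, interaction power is 23% at 0.05. For 12 and 2 points it is 52%.

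**5. Size of the complement.** Protocol 13.1 expects up to 10% of control participants to receive neither test. If that approximates those with no symptoms, no serious illness and no advanced disease (an assumption), it is 0.10 × 586 ≈ 59 per arm. At 19% vs 26% the 95% CI would be 1.96 × √(0.3463 / 59) ≈ ±15 points.

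**The case against.** **The plan states no misleading rule.** A reader might infer that the SAP commits to separate tests in each stratum and will read significant-versus-not as effect modification. The text does not go that far. SAP 8.1 gives no within-stratum test or threshold of its own, 95% CIs are planned, and SAP 6.3 does not say whether its comparisons are within or between subgroups. This stands: the misreading is a risk left open. What remains is that no method is given that answers the stated hypothesis.

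**The symptomatic or severely ill subgroup is not where the strategies diverge.** A reader might infer that it is. It is where they are most alike, since control participants with symptoms qualify for sputum Ultra and AlereLAM, and those with advanced disease or serious illness for AlereLAM. The larger contrast in testing is in the complement. Nor is most of the gain expected from universal testing: Protocol 13.1 attributes about 1 of the 7 points to it (19% to 20%) and about 6 to urine and stool Ultra.

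**The SAP did not drop the subgroup on its own.** Protocol 13.2.3 already omits it, so the inconsistency begins within the Protocol.

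**Baseline data exist.** WHO symptom screening is scheduled at Day 0 in both arms. SAP 4.4 lists WHO stage and CD4, and SAP 7.2 leaves some derived variables to later versions. This stands, and it makes the repair easy.

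**The remedy has low power, and SAP 6.3 reserves inference for the primary objective.** Both are true. They favour presenting the interaction as an estimate with its interval. They do not make stratum-specific p-values informative about a difference in effects.

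**Conclusion.** The concern holds in a limited form. The SAP states an effect-modification hypothesis for CD4 and country but specifies no interaction, so as written it cannot test it. With a constant 7-point effect, the two strata would disagree at the 0.01 level in about 40% to 43% of trials. In the hypothesised direction the figure is 9% to 27%, or 20% at an equal split. The total should not be read as the rate of false support, because the rest of the disagreement runs the other way.

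These figures rest on two strata, an assumed low-CD4 share of 30% to 60%, and confirmation rates of 19% and 26%. The primary endpoint also requires treatment started within 72 hours, so its rates may be lower. The hypothesis in SAP 8.1 is itself worded in terms of confirmation, so the endpoint to which it applies needs stating.

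Separately, the synopsis disagrees with Protocol 13.2.3 and SAP 9 on the symptom and severity subgroup. The primary test, sample size and primary conclusion are unaffected.

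**What to change.** 1. In SAP 8.1 and 9, report for the primary endpoint the treatment-by-factor interaction on the risk-difference scale, with a 95% CI and one p-value per factor, for CD4, country, viral load and sex. Show subgroup estimates with intervals and make no significance claim within a subgroup.
2. Fix one CD4 definition before database lock, reconciling Protocol 13.2.3, SAP 7.2 and SAP 11, and remove the option to refine the bands on observed frequencies for this analysis.
3. Reconcile the synopsis with Protocol 13.2.3 and SAP 9 on the subgroup with any TB symptoms, severe illness or advanced HIV disease. Report it beside its complement (none of the three). Define both from the Day 0 WHO symptom screen, baseline examination, WHO stage and baseline CD4, not from the in-hospital symptom fields. Add the Day 0 symptom variables to SAP 4.4.
4. State that these analyses are estimation and not powered tests.

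**Cost:** SAP wording, a synopsis-to-body reconciliation in the Protocol, and a few model terms. No new data collection is needed, because the Day 0 assessments are already scheduled. The downside is imprecision: about ±9.5 points for an interaction with equal halves and no loss, and wide intervals in what may be a small complement.

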### 8.2 Secondary Efficacy Analyses

All secondary efficacy analyses will be calculated on ITT and Per protocol populations. The Secondary Efficacy Analyses are:

8.2.1 We will compare the proportion of deaths during eight weeks after enrolment between all participants enrolled in two study groups. We will test this differences using the test statistics  $z$  has an asymptotic standard normal distribution. These groups are microbiologically confirmed TB and therapy initiated within 72 hours from admission (numerator/success) and non-lab-confirmed TB or therapy not initiated within 72 hours (denominator/failure). We will compare, using Chi-square test or Fisher Test, these proportion values between intervention and control group.

8.2.2 We will estimate the Kaplan Meier curves to assess time to TB treatment initiation among those with microbiologically confirmed TB and among all TB (also including clinically diagnosed). We will compare both arms using the log rank test. We will use the KM procedure to calculate the survival rate from the survival function. If deemed necessary, to study the effects of some covariates and start of treatment over time we will use the Cox regression.

8.2.3 We will compare the proportion of cases re-admitted to hospital, to test this proportion we calculate the number of admissions after initial discharge and within 8 weeks from enrolment from all participants enrolled. We will compare, using Chi-square test or Fisher Test, these proportion values between intervention and control group.

8.2.4 We will compare the proportion of participants who are diagnosed with TB (irrespective of bacteriological confirmation and are started on TB treatment within 72 hours of enrolment). We will compare, using Chi-square test or Fisher Test, these proportion values between intervention and control group.

8.2.5 We will calculate the proportion of participants who are diagnosed with microbiologically confirmed TB and are started on TB treatment at 7d, 14d, 4 and 8 weeks of enrolment. We will compare, using Chi-square test or Fisher Test, these proportion values between intervention and control group.

